3.4. Enrollment Strategy

Study subjects will be recruited from the Institution/clinical site's subject database and/or utilizing Independent Ethics Committee (IEC) or Institutional Review Board (IRB) approved materials.

4. STUDY DESIGN AND RATIONALE

4.1. Description of Study Design

This will be a pilot, one-visit, open-label, non-dispensing study. Subjects will be given instructions and then attempt to insert and remove a contact lens in each eye.

4.2. Study Design Rationale

The results from this pilot study will help design future studies and product development strategy for a senior subject demographic.

4.3. Enrollment Target and Study Duration

The population to be studied will be healthy male and female volunteers (at least 60 years old) who are not habitual wearers of contact lenses (approximately 50% will be neophytes and approximately 50% will have had some previous experience with contact lens wear). A minimum of 12 and a maximum of 16 subjects will be enrolled.

The study is scheduled for one visit on one day:

Visit 1: (Day 0): Baseline Screening, Insertion and Removal Training, Insertion and Removal Attempts, Exit

5. TEST ARTICLE ALLOCATION AND MASKING

5.1. Test Article Allocation

This is a one-visit, non-randomized, open label pilot study. One test article (ACUVUE OASYS® 1-DAY with HydraLuxe™ Technology) will be used. No randomization scheme will be used.

5.2. Masking

This is an open-label study. Subjects who are discontinued will not be replaced.

5.3. Procedures for Maintaining and Breaking the Masking

Not applicable

6. STUDY INTERVENTION

6.1. Identity of Test Articles

The following contact lenses will be used in this study:

Table 1: Test Articles

Test Article	
Name	ACUVUE OASYS® 1-DAY with HydraLuxe™ Technology
Manufacturer	J&J Vision Care
Lens Material	senofilcon A
Nominal Base Curve @ 22°C	8.5
Nominal Diameter @ 22°C	14.3
Nominal Distance Powers (D)	+1.00
Wear Schedule in Current Study	Daily wear
Replacement Frequency	Daily disposable
Packaging Form (vial, blister, etc.)	Sterile blister pack

6.2. Ancillary Supplies/Products

The following solutions will be used in this study:

Table 2: Ancillary Supplies

Solution Name/Description	EyeCept
Manufacturer	Optics Laboratory, Inc.
Preservative	None
Other distinguishing items (dye, packaging, approval status, etc.)	NA

6.3. Administration of Test Articles

Test articles will be given to subjects meeting all eligibility requirements. Subjects will only be attempting to insert and remove test articles during the non-dispensing visit. Multiple test articles may be dispensed during the insertion and removal process if the lens needs to be replaced at the discretion of the Investigator due to excessive handling. Lost or damaged test articles may be replaced at the discretion of the Investigator and/or the Sponsor.

6.4. Packaging and Labeling

The test articles will remain in their marketed packaging and labeling.

6.5. Storage Conditions

Test articles will be maintained at ambient temperatures at the clinical site. Test articles must be kept under secure conditions.

6.6. Collection and Storage of Samples

Used lenses will not be collected or stored.

When possible, any lens or test article associated with an Adverse Events and/or a Product Quality Complaint must be retained and stored in a glass vial with moderate solution pending directions from the sponsor for potential return back to JJVC.

6.7. Accountability of Test Articles

JJVC will provide the Investigator with sufficient quantities of study articles and supplies to complete the investigation. The Investigator is asked to retain all lens shipment documentation for the test article accountability records.

Test article must be kept in a locked storage cabinet, accessible only to those assigned by the Investigator for dispensing. The Investigator may delegate this activity to authorized study site personnel listed on the Site Delegation Log. All test articles must be accounted. This includes:

1. What was dispensed for the subject for trial fitting, to wear out of the office, or issued for the subject to replace appropriately between visits
2. What was returned to the Investigator unused
3. The number and reason for unplanned replacements

The Investigator will collect all unused test articles from the subjects at the end of the subject's participation. Following final reconciliation of test articles by the monitor, the Investigator or monitor will return all unused test articles to JJVC.

If there is a discrepancy between the shipment documents and the contents, contact the study monitor immediately.

Reference [REDACTED] Site Instructions for Test Article Receipt and Test Article Accountability for additional information.

7. STUDY EVALUATIONS

7.1. Time and Event Schedule

Table 3: Time and Events

Visit Information		Visit 1 (Day 0)	
Estimated Visit Duration		2 Hours	
Event	Baseline	Trial #1 Dispense	Post Lens Removal
Study Informed Consent	X		
Demographics	X		
Medical History	X		
Eligibility Assessment	X		
Subject Reported Symptoms		X	
Distance Visual Acuity	X		X
Spherocylindrical Refraction & VA	X		
Biomicroscopy & Eye Rinse	X		X
Study Lens Insertion & Removal		X	
Study Completion			X

7.2. Detailed Study Procedures

VISIT 1

Screening Visit, Baseline Evaluation, Dispensing Visit.

Visit 1: Screening		
Step	Procedure	Details
1.1	Statement of Informed Consent	
Each subject must read, understand, and sign the Statement of Informed Consent before being enrolled into the study. The Principal Investigator or his/her designee conducting the informed consent discussion must also sign the consent form.
 
Note: The subject must be provided a signed copy of this document.

1.2	Demographics	Record the subject's year of birth, gender, race and ethnicity.
1.3	Medical History and Concomitant Medications	Questions regarding the subjects' medical history and concomitant medications.
1.4	Eligibility after Baseline	
All responses to Inclusion Criteria questions must be answered "yes" and all responses to Exclusion Criteria questions must be answered "no" for the subject to be considered eligible.
 
If subject is deemed to be ineligible after screening, proceed to Final Evaluation and complete all forms.

Visit 1: Baseline		
Step	Procedure	Details
1.5	Distance visual acuity (VA)	Record the distance Snellen VA for OD, OS and OU with habitual refractive correction. Subject must keep reading smaller lines until less than half the letters are correctly identified
1.6	Subjective spherocylindrical refraction and VA	Perform binocular subjective best spherocylindrical refraction and record the best corrected VA for OD, OS and OU.
1.7	Biomicroscopy	FDA Slit Lamp Classification Scale will be used to grade the findings and determine eligibility. If any of these slit lamp findings are Grade 3 or higher, the subject is discontinued from the visit as ineligible and may be rescheduled for another baseline visit for the randomization period.

Visit 1: Baseline		
Step	Procedure	Details
1.8	Eye Rinse	
The investigator or technician may rinse the subject's eyes thoroughly with study provided solution.

1.9	Eligibility after Baseline	
All responses to Inclusion Criteria questions must be answered "yes" and all responses to Exclusion Criteria questions must be answered "no" for the subject to be considered eligible.
 
One additional baseline examination is permitted to be performed if the subject does not meet the eligibility criteria at the initial baseline visit
 
If subject is deemed to be ineligible after baseline, proceed to Final Evaluation and complete all forms.

Visit 1: Treatment 1		
Step	Procedure	Details
1.10	Lens Insertion and Removal Instructions	
The subject will be given instructions on contact lens insertion and removal. A video may be used (https://www.acuvue.ca/contact-lens-care/how-to-put-in-and-take-out-contacts) in addition to verbal instructions.

1.11	Lens Insertion	
The subject will attempt to insert a contact lens in each eye. After the initial instructions are given to the subject, the lens will be assigned and the starting time should be recorded prior to attempting to apply a lens to each eye.
 
If a subject has not successfully inserted a lens in the first eye after 20 minutes, they can stop the process on the first eye and attempt to insert a lens on their fellow eye.
 
If a subject has not successfully inserted a lens in the fellow eye after 20 minutes, they can stop the process and proceed to the Exit Visit.
 
The subject will be allowed to voluntarily end the contact lens insertion activity at any time prior to the 20-minute time point.
 
Record the time of insertion for each eye or the time of stopping the insertion process for each eye.
 
After the subject has successfully inserted a lens in

Visit 1: Treatment 1		
Step	Procedure	Details
		
the first eye, they can attempt to insert a lens on their fellow eye following the same guidelines and instructions as the first eye.
 
Note: A Patient Instruction Guide will be given to the subject in any study where a lens is placed on eye. The subject may wear the study lenses only at the clinical site.

1.12	Subject Reported Ocular Symptoms	Subjects will respond to a verbal open-ended symptoms questionnaire.
1.13	Lens Removal	
The subject will attempt to remove a contact lens from each eye. After the initial instructions are given to the subject, the starting time should be recorded prior to attempting to remove the contact lens from each eye. A video may be used (https://www.acuvue.ca/contact-lens-care/how-to-put-in-and-take-out-contacts) in addition to verbal instructions.
 
After the subject has successfully removed a lens from the first eye, they can attempt to remove the lens from their fellow eye following the same guidelines and instructions as the first eye.
 
If a subject has not successfully removed the contact lens from the first eye after 20 minutes, the doctor or technician can remove both lenses for the subject and then have them proceed to the Exit Visit.
 
Record the time of removal for each lens or the time of stopping the removal process for each lens
 
All worn lenses will be discarded

FINAL EVALUATION

The final evaluation will ordinarily take place immediately following the last scheduled follow-up visit per the study protocol. It may also take place at any point the subject discontinues the study or is terminated from the study.

Final Evaluation		
Step	Procedure	Details
	Final Exam Form	Indicate if the subject completed the study successfully. If subject discontinued from the study, indicate the reason.

Final Evaluation		
Step	Procedure	Details
	Subjective spherocylindrical Refraction and Visual Acuity	Perform bare-eye subjective spherocylindrical refraction with a phoropter and record the best corrected distance visual acuity to the nearest letter (OD, OS, and OU). [REDACTED]
	Exit Slit Lamp Biomicroscopy	FDA Slit Lamp Classification Scale will be used to grade the findings. If the clearance of the fluorescein needs to be expedited, preservative-free rewetting drops or saline may be instilled. [REDACTED]
	Signature	Record any additional information on the page provided and sign the form. [REDACTED]

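### The only scheduled symptom question comes before lens removal, and subjects who fail fellow-eye insertion may bypass it

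*Combined protocol and SAP*

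**What the plan says.** The protocol's Section 7.2 runs the treatment part of the visit in four numbered steps: instruction (1.10), insertion (1.11), symptoms (1.12) and removal (1.13). Step 1.12 reads in full: "Subjects will respond to a verbal open-ended symptoms questionnaire". Step 1.13 then begins: "The subject will attempt to remove a contact lens from each eye".

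Step 1.11 gives these routes out of insertion:

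- First eye not achieved after 20 minutes: "they can stop the process on the first eye and attempt to insert a lens on their fellow eye".
- Fellow eye not achieved after 20 minutes: "they can stop the process and proceed to the Exit Visit".
- Early stop: "The subject will be allowed to voluntarily end the contact lens insertion activity at any time prior to the 20-minute time point". The next step after an early stop is not stated.

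In Step 1.13, if first-eye removal has not succeeded after 20 minutes, "the doctor or technician can remove both lenses for the subject and then have them proceed to the Exit Visit".

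Table 3 (Section 7.1) has one mark in the row "Subject Reported Symptoms", in the Trial #1 Dispense column. The Post Lens Removal column is marked for visual acuity, biomicroscopy and study completion, but not for symptoms. The Final Evaluation table begins with a form ("Indicate if the subject completed the study successfully") and continues with refraction and acuity, exit slit lamp and signature. It lists no symptom item.

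**The concern.** The study asks whether people aged 60 or over can put a lens in and take it out, and Section 4.2 says the results will inform later studies and product strategy. How the eyes feel after both tasks is useful information for that purpose. As scheduled, the one enquiry falls between the two tasks, so nothing visible in the plan asks about symptoms during or after removal.

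The enquiry is also partly conditioned on the result of the first task, because one group of insertion failures may leave before reaching it. Section 14.1 summarises safety variables by previous wearing experience, and Section 14.9 imputes nothing. If neophytes and previous wearers fail insertion at different rates, a symptom table split by experience would compare groups that were selected differently.

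What is at stake is the completeness of the tolerability description. The primary endpoint, overall success of insertion and removal, does not use the symptom answers.

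**Working it through.** **1. The plan's own figure.** Figure 1 allows 20 minutes per attempt and a total of 80 minutes. 20 min × 2 tasks × 2 eyes = 80 min, which reproduces. There is no sample size or power calculation to check; Section 14.2 says none was done.

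**2. Who reaches Step 1.12, and when.** Tracing the routes in Steps 1.11 to 1.13:

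| Subject's course | Reaches Step 1.12? | Scheduled question after the last handling? |
|---|---|---|
| Both lenses inserted, both removed | Yes, before removal | None visible |
| Both inserted, first-eye removal fails, staff remove both | Yes, before removal | None visible |
| First eye fails, fellow eye succeeds | Yes; no exit route applies | None visible after removal |
| Fellow eye fails at 20 minutes, with or without a first-eye lens in | May be bypassed | None visible if bypassed |
| Voluntary early stop | Not stated | Not stated |

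**3. Maximum handling time under the 20-minute limits.**

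- Eye that fails insertion: at most 20 min; a subject who fails both eyes, 20 + 20 = 40 min.
- Eye that is inserted and then removed by the subject: at most 20 + 20 = 40 min; both eyes, 80 min.
- Subject with both lenses in who fails first-eye removal: 20 + 20 + 20 = 60 min.

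The highest ceiling belongs to eyes that go on to removal. For those eyes, up to 20 of the 40 minutes come after the only question.

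**4. Illustrative number without an answer.** The rate of bypassing Step 1.12 is not in the documents. I assume f = 10%, 25% or 50% and take N = 12 and 16 from Section 14.2. Expected number skipped = N × f. Number asked, m = N minus that figure rounded. If none of m subjects reports a symptom, the one-sided 95% exact upper bound on the symptom rate is 1 − 0.05^(1/m).

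| N | f (assumed) | N × f | m | Upper bound |
|---|---|---|---|---|
| 12 | 0 | 0 | 12 | 22.1% |
| 12 | 10% | 1.2 | 11 | 23.8% |
| 12 | 25% | 3 | 9 | 28.3% |
| 12 | 50% | 6 | 6 | 39.3% |
| 16 | 0 | 0 | 16 | 17.1% |
| 16 | 10% | 1.6 | 14 | 19.3% |
| 16 | 25% | 4 | 12 | 22.1% |
| 16 | 50% | 8 | 8 | 31.2% |

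The bound shows only the loss of numbers. It treats those asked as representative, which is doubtful when being asked depends partly on insertion success.

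**5. Whether other records fill the gap.** The exit slit lamp grades signs, not complaints. Section 13.3 requires all adverse events to be documented, but the item to be recorded is a diagnosis rather than a symptom, and no time point for asking is given. The unscheduled-visit table (Section 7.3) does script a chief-complaint item and an adverse event review; the Final Evaluation table lists neither, and Section 14.1 excludes unscheduled visits from the analysis.

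**The case against.** The case for leaving the plan alone has real weight. Symptoms are not an endpoint, there is no hypothesis, and Sections 14.6 and 14.7 plan no secondary or exploratory analysis. This is a single-visit pilot of a marketed lens, and adverse event recording and exit biomicroscopy remain. That stands, and it limits the point to an inexpensive improvement.

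The timing rests on step numbers alone. The Table 3 column holding the symptom mark also holds insertion and removal together, so the table shows one assessment during the trial period without placing it before removal. This stands too, although the empty Post Lens Removal cell and the Final Evaluation list agree with the step order.

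The exit wording is permissive and loosely drafted. Read literally, a subject with a lens in the first eye who fails the fellow eye would go to exit past the removal step; those passages need reconciling. If such a subject counts as discontinued, Section 8.2 has the investigator complete the current visit, which might bring Step 1.12 back. So bypassing is allowed by the text, but not certain.

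Some content cannot be seen. Figure 1 has subjects fill out a final evaluation form whose content is not described, and the symptom procedure in Appendix D is redacted. Appendix A lists no study questionnaires, which leaves the question open. The claim can only be that no scheduled question is visible.

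A reader might also infer that the bypassed subjects have the most handled eyes, that removal is the more irritating task, or that discomfort will be understated. The documents support none of these. The time limits point the other way on handling, no passage ranks the tasks by irritation, and the direction of any bias is unknown.

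**Conclusion.** The point holds in a limited form. Followed as written, the plan produces a symptom summary taken before removal and partly conditioned on insertion success, with no visible scheduled question after up to 20 minutes per eye of removal attempts. This applies to every subject who reaches removal. The bypass is narrower: it concerns fellow-eye failures at 20 minutes, and possibly early stoppers, whose route is not stated.

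It would go too far to say that all insertion failures are never asked. First-eye-only failures still reach Step 1.12, and the exit is optional. The counts of 1 to 6 of 12 or 2 to 8 of 16 are illustrations that assume a 10% to 50% bypass rate, not estimates. The conclusion also assumes that the steps are done in numbered order and that neither the undescribed final form nor the redacted procedure contains a post-removal symptom question. The importance is low: the change is worth making because it is cheap, and the primary success rate does not depend on it.

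**What to change.** - Repeat the existing open-ended question at Final Evaluation for every subject who attempted insertion, whatever the outcome. Ineligible subjects, who are also sent to Final Evaluation, would not need it.
- Add the matching mark under Post Lens Removal in Table 3.
- State in Step 1.11 whether subjects who stop or fail there complete Step 1.12.
- In Section 14, summarise the exit answers descriptively by insertion and removal outcome, separately from the Step 1.12 answers.

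If the final evaluation form or the redacted procedure already asks about symptoms after removal, saying so in Section 7.2 and Table 3 would be enough for the first two items.

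The cost is one or two minutes per subject with an existing instrument, one table entry and one more descriptive table. With 12 to 16 subjects, the cells by outcome will be small and should be shown as counts without inference.

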- 20 minutes given for both insertion and removal attempts for both eyes = total trial time of 80 minutes
- Technician will record success or failure for insertion and removal for OD and OS

Final Evaluation

- Subject will fill out final evaluation form

COMMONLY USED ABBREVIATIONS AND DEFINITIONS OF TERMS

ADE	Adverse Device Effect
AE	Adverse Event/Adverse Experience
BCVA	Best Corrected Visual Acuity
BSCVA	Best Spectacle Corrected Visual Acuity
CFR	Code of Federal Regulations
COM	Clinical Operations Manager
CRA	Clinical Research Associate
CRF	Case Report Form
CRO	Contract Research Organization
CTP	Clinical Technical Procedure
D	Diopter
DMC	Data Monitoring Committee
eCRF	Electronic Case Report Form
EDC	Electronic Data Capture
FDA	Food and Drug Administration
GCP	Good Clinical Practice
HIPAA	Health Insurance Portability and Accountability Act
IB	Investigator's Brochure
ICF	Informed Consent Form
ICH	International Conference on Harmonization
IEC	Independent Ethics Committee
IRB	Institutional Review Board
ISO	International Organization for Standardization
JJVC	Johnson & Johnson Vision Care, Inc.
OD	Right Eye
OS	Left Eye
OU	Both Eyes
PD	Protocol Deviation
PI	Principal Investigator
PIG	Patient Instruction Guide
PQC	Product Quality Complaint
PRO	Patient Reported Outcome
QA	Quality Assurance
SAE	Serious Adverse Event/Serious Adverse Experience
SAS	Statistical Analysis System
SD	Standard Deviation
UADE	Unanticipated Adverse Device Effect
USADE	Unanticipated Serious Adverse Device Effect
VA	Visual Acuity

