2.2. Endpoints

Primary Endpoint(s)

Overall success rate (as a percentage) of insertion and removal of a contact lens in both eyes.

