8. SUBJECTS COMPLETION/WITHDRAWAL

8.1. Completion Criteria

Subjects are considered to have completed the study if they:

- provided informed consent
- they are eligible
- completed all scheduled visits.

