14.3. Analysis Populations

Safety Population:

All subjects who were administered any test article excluding subjects who drop out prior to administering any test article. At least one observation should be recorded.

Per-Protocol Population:

All subjects who have successfully completed all visits and did not substantially deviate from the protocol as determined by the trial cohort review committee prior to database hard lock (Per-Protocol Population). Justification of excluding subjects with protocol deviations in the Per-Protocol Population set will be documented in a memo to file.

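### Does the untried second eye after a failed first lens removal leave the endpoint undefined?

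*Combined protocol and SAP*

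**What the plan says.** Figure 1, under Trial Period, sets the time: "20 minutes given for both insertion and removal attempts for both eyes = total trial time of 80 minutes". It also sets the record: "Technician will record success or failure for insertion and removal for OD and OS".

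Section 7.2, Step 1.13, begins in the same way: "The subject will attempt to remove a contact lens from each eye". It then describes the fellow-eye attempt as following a successful first removal. For a first eye that has not succeeded by 20 minutes, it says that "the doctor or technician can remove both lenses for the subject and then have them proceed to the Exit Visit". The data item is "Record the time of removal for each lens or the time of stopping the removal process for each lens".

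The only endpoint, in Section 2.2, is "Overall success rate (as a percentage) of insertion and removal of a contact lens in both eyes". Section 2.3 has no hypotheses, and Sections 14.6 and 14.7 plan no secondary or exploratory analyses. Section 14.1 promises descriptive tables by previous wearing experience, with percentages of subjects or of eyes. Section 14.9 does not impute missing values, but counts them.

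**The concern.** Figure 1 appears to require a removal result from each eye, while Step 1.13 lets staff end the session with one eye untried. That eye then fits neither record neatly. Figure 1 offers only success or failure, and Step 1.13 asks for a removal or stopping time although the subject never began. Section 14.9 helps only if the eye is first classed as missing, and nothing classes it so.

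If one analyst left the eye missing and another counted it as a non-success, they could report different removal rates. The wearing-experience groups hold only about 6 to 8 subjects, so one eye is visible in a percentage. Because the exit is optional, similar subjects could also yield different data depending on what the site did. The stated purpose of the study is to inform later designs, so a blurred removal rate would be unwelcome.

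**Working it through.** **Inputs.** 20 minutes per attempt, two tasks, two eyes (Figure 1); 12 to 16 subjects, about half in each experience group (Synopsis, Section 4.3), hence groups of about 6 to 8. The documents give no expected failure rate, so the number of affected subjects is an assumption.

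**1. Time.** Figure 1: 2 tasks × 2 eyes × 20 = 80 minutes, which reproduces the stated total. Step 1.13 exit: 2 × 20 for insertion + 1 × 20 for the first removal = 60 minutes at most. The 80 minutes is time given, not time that must be used. Quick success shortens the session, and Step 1.11 lets a subject stop inserting before 20 minutes. So 60 within 80 is no contradiction.

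**2. Sequence.** Step 1.13 read as a whole has a general statement (each eye), a route after first-eye success (go on to the fellow eye), and a permitted exit after first-eye failure. Figure 1 summarises the main route and omits the exception.

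**3. Endpoint, per subject.** Success needs both tasks in both eyes. With n subjects in a group and one who fails the first removal, all others succeeding, the rate is (n − 1)/n whatever the second eye is called:

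- n = 6: 5/6 = 83.3%
- n = 8: 7/8 = 87.5%

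**4. A per-eye removal table, if one were made.** Same assumptions, with every lens inserted.

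| Group | Untried eye missing, (2n − 2)/(2n − 1) | Untried eye a non-success, (2n − 2)/2n |
|---|---|---|
| n = 6 | 10/11 = 90.9% | 10/12 = 83.3% |
| n = 8 | 14/15 = 93.3% | 14/16 = 87.5% |

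For the whole sample with k such subjects, the rates are (2n − 2k)/(2n − k) against (2n − 2k)/2n:

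- n = 12, k = 1: 22/23 = 95.7% against 22/24 = 91.7%
- n = 12, k = 4: 16/20 = 80.0% against 16/24 = 66.7%
- n = 16, k = 1: 30/31 = 96.8% against 30/32 = 93.8%
- n = 16, k = 4: 24/28 = 85.7% against 24/32 = 75.0%

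The gap is about 3 to 13 percentage points for k = 1 to 4, and zero for k = 0.

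**5. Does the subject stay in the denominator?** Dropping the affected subject would give 11/11 = 100% instead of 11/12 = 91.7% (n = 12, k = 1). Nothing in the plan calls for that. Section 8.1 defines completion by consent, eligibility and having "completed all scheduled visits", not by handling the lens well. The Safety Population is "All subjects who were administered any test article excluding subjects who drop out prior to administering any test article", which keeps the subject in. The Per-Protocol Population removes substantial deviations, and an exit that Step 1.13 allows is not a deviation. Nor is the subject's result missing: one observed failure settles it, so Section 14.9 is not engaged.

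**The case for a change.** The strongest case is that the plan never states the unit of the endpoint. Section 14.5 reads Not Applicable, and Section 14.1 speaks of results for each subject or eye. If the rate were taken over eyes, the coding would reach the endpoint itself. Under the assumptions above, the gap would be that of step 4. A literal reader might even enter the time at which staff took the lens out as a removal time.

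Part of this stands. No passage codes an untried eye, and Figure 1 does not repeat the Step 1.13 exception. An eye whose insertion failed raises the same question about its removal entry. But the endpoint asks for success in both eyes, which is most naturally a property of the subject. If someone did tabulate eyes, Figure 1's two-way record already points to the answer: a lens that staff took out was not removed by the subject, so the entry is failure. The larger gaps arise only if an analyst sets that record aside and treats the eye as missing. The electronic case report form is not among the documents and may already carry a code. Variation between sites is real, but it comes from the discretion that Step 1.13 gives, and it does not alter the subject's result.

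**Conclusion.** The concern does not call for a change. Figure 1 is a summary that leaves out a stated exception, and the missing code is a detail that an analyst fills sensibly as a non-success. The effect on the both-eyes rate per subject is nil. A per-eye removal rate could differ by about 3 to 13 points over the whole sample for one to four affected subjects. That requires a table the plan does not name, a missing coding that its records do not suggest, and success in every other attempt. With no hypothesis to test and results that are purely descriptive, writing the convention down would not change what the study reports. The conclusion rests on reading the endpoint per subject and on keeping every subject who attempted the task in the denominator. It implies no view on when staff should remove a lens.
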